- Indication for Use: The SNS CVS-M Device is specifically indicated to treat episodic Migraine Headache pain.

2) Patient Selection Criteria Pre-Treatment Data

In working with and through their respective designated Pivotal Study assistant(s)/coordinator(s), the Investigators will identify and screen potential participants, all of whom will have previously been diagnosed as episodic migraine patients. The Investigators will review the patients' medical records to select those individuals whom they identify as meeting the inclusion criteria for participating in the Study.

- **Inclusion Criteria:** Each participant must have a Pre-Treatment History that, when initially screened by a Pivotal Study Investigator or designee, documents that she/he meets all elements of the following:
 - The patient must have been diagnosed with episodic Migraine Headache at least six months prior to entering into the Study, consistent with the International Headache Classification of Headache Disorders-II (ICHD-II) guidelines.
 - The patient must have a history of at least three consecutive months of stable Migraine Headaches prior to entering the Study. The patients will not have had changes in medication usage for the three Months leading up to the Study, nor will they introduce new medications during the Study period. Patients will satisfy these criteria: On a Monthly basis, at least four, and not more than a total of fourteen (4-14), Headache Days of which between four and fourteen (4-14) are Migraine Headache Days.
 - The patient must not have failed on more than two classes of properly administered prophylactic pharmaceutical therapies for migraine headache. The patient may be on a single migraine prophylactic as long as the dosage has not been altered within three months of starting the Study and the dosage must not be altered for the duration of the Study;
 - The Investigator must have confidence in the patient's ability to reliably use the CVS-M Device and promptly complete the Daily Headache Diary forms and promptly return them to the Study coordinator. That Daily Headache Diary will be completed from the beginning of the Pre-Treatment Baseline Period through the end of the Pivotal Study. It is described more fully below and in the Definitions section at the end of this document.
- **Exclusion Criteria**: Individuals who:
 - o are pregnant
 - have a history of cardiovascular disease
 - work night shifts
 - o have been diagnosed with vestibular migraine

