Block randomization with a block size of four (4) will be used at each site. Each site will receive sets of well-shuffled envelopes in packets of four. A given packet will be completed before the next packet is opened. Each packet of four will contain two cards specifying that a subject should be in the active treatment arm and two cards specifying the placebo arm. This procedure results in six possible different arrangements, for four patients, of the ordering of treatment and placebo assignments. The unblinded Pivotal Study coordinator will record the patient's designation but will not share the assignment with the patient, Investigator, or Statistician.

4) Pivotal Study Schedule; Subject Enrollment and Activities; Monitoring

The Pivotal Study Period will last one hundred and twelve days, beginning with a Pre-Treatment Baseline Period of one Month (28 days), at the end of which the Investigator will reconfirm the appropriateness of the subject's participation in the Pivotal Study, followed by a Treatment Period of three Months (84 days).

As noted, subjects will be advised that during the Pivotal Study Period they may maintain patterns of usage of approved therapeutic medications that they normally use and that they should not initiate new medications, medicating patterns or other interventions. Accommodations for rescue medications will be made, using pharmaceuticals from an approved list developed by the Investigators.

Potential participants will be required to keep a Daily Headache Diary throughout the Pivotal Study Period and, *inter alia*, to document times of CVS-M treatments. They will enter the Daily Headache Diary information using a computer-based system.

The phases and activities of the Pivotal Study are listed below:

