- (i) Screening & Baseline Period: Once the subject has been established as having the appropriate Pre-Treatment History, she/he will be asked to complete a review of the informed consent. If the subject agrees to participate in the Pivotal Study, the subject will then complete a Screening Visit. If the subject is recommended for continuation in the Study after the Screening Visit and tentatively approved by an Investigator, she/he will start a Daily Headache Diary and continue to make entries for twenty-eight consecutive days. The Pivotal Study coordinator will complete a Headache History Questionnaire for the subject. The subject will undergo a Vestibular Testing Procedure to establish a baseline record. Any abnormality identified during the Vestibular Testing Procedure for a potential subject will be reported both to the relevant Investigator and to the Vestibular System Coordinator, either of whom can disqualify such potential subject from participating in the Pivotal Study.
- (ii) Clinic Period: After enrollment, the completion of one Month of Daily Headache Diary entries, and reconfirmation by the relevant Investigator of the subject's participation in the Pivotal Study, the subject will come to the clinic for appointments for two days (within the same week) for treatments and for training with respect to use of the CVS-M Device. During the first clinic visit, the subject will complete a Quality of Life and Cognition Assessment exam. Also, women of childbearing age will complete a urine-based pregnancy test to reconfirm that they are not pregnant. The local Pivotal Study coordinator will open, at random, an envelope assigning the patient to the treatment arm or the placebo arm. The second clinic day may be skipped if the Study Coordinator feels that the patient is prepared to use the CVS-M device properly (this should be confirmed with a phone call on the second day). The clinic period is described below.

On each visit during the clinic period, the subject will receive a treatment and be instructed in how to self-administer a defined, controlled treatment using

Version 072414 Schulman Version 4

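### Fixed, disclosed blocks of four let the unblinded coordinator foresee about one third of assignments, and no opening order is set within a packet

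*Combined protocol and SAP*

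**What the plan says.** All references are to the combined protocol and SAP.

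- **Block structure (section 3).** "Block randomization with a block size of four (4) will be used at each site". The 2:2 content is also stated: "Each packet of four will contain two cards specifying that a subject should be in the active treatment arm and two cards specifying the placebo". The envelopes are mixed by hand: "Each site will receive sets of well-shuffled envelopes in packets of four". Packets are used one after another: "A given packet will be completed before the next packet is opened".
- **Who knows the assignments (section 3).** Only the site coordinator opens the envelopes. "The unblinded Pivotal Study coordinator will record the patient's designation but will not share the assignment with the patient, Investigator, or Statistician".
- **How an envelope is picked (section 4(ii), Clinic Period).** After the baseline month and the Investigator's reconfirmation, "The local Pivotal Study coordinator will open, at random, an envelope assigning the patient" to an arm.
- **The coordinator's part in selection (section 2).** "In working with and through their respective designated Pivotal Study assistant(s)/coordinator(s), the Investigators will identify and screen potential participants".

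The documents describe no generated list, envelope numbering, opening log or central holder of the sequence. They do provide for the coordinator's record of each designation (section 3), device files of the temperatures actually delivered (section 4(ii)) and an independent audit of sites (section 10).

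**The concern.** Allocation concealment must hold until a patient's entry is settled. Here the block size and its 2:2 content are printed in the protocol, packets run strictly one after another, and one person at each site has seen every earlier assignment. Towards the end of a packet that person can know the next arm for certain.

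The same person works with the Investigator on screening and runs the clinic visits. Entry includes matters of judgement, such as the Investigator's confidence that the patient will use the device and diary reliably (section 2). Timing is flexible too: the Definitions allow a few days for re-confirmation and ignore gaps due to clinic scheduling. Changing which of two eligible patients attends first changes who receives a known assignment, without breaching any criterion.

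What is at stake is selection bias in a comparison of about 80 patients whose headaches are classified by their own judgement (Definitions, Migraine Headache). The second issue is verification. With no set order within a packet, there is nothing to check the order of opening against.

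**Working it through.** **Inputs.** Block size 4, two per arm, packets finished in turn, coordinator sees all assignments (section 3); 80 planned completers (section 3); six entries in the site list (Definitions).

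**Step 1: the plan's own figure.** The number of orderings of two active (A) and two placebo (P) is C(4,2) = 6. This matches the plan: "This procedure results in six possible different arrangements, for four patients, of the ordering of treatment and placebo assignments".

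**Step 2: assignments that are certain beforehand.** An assignment is certain when the earlier ones in the packet have used up one arm.

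| Ordering | Certain positions | Count |
|---|---|---|
| AAPP | 3, 4 | 2 |
| APAP | 4 | 1 |
| APPA | 4 | 1 |
| PAAP | 4 | 1 |
| PAPA | 4 | 1 |
| PPAA | 3, 4 | 2 |

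The total is 8 of 24 assignments, or 33.3%. By position the chances are 0, 0, 1/3 and 1, which sum to 4/3 per packet.

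**Step 3: best-guess accuracy.** Always guessing the arm with more cards left is right with chance 1/2, 2/3, 2/3 and 1 by position. The sum is 17/6, and (17/6)/4 = 17/24 = 70.8%, against 50% with no knowledge.

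**Step 4: scale to 80 patients.** With 20 complete packets, 20 × 4/3 = 26.7 certain assignments. Partial packets lower this. A site that ends with 1, 2 or 3 patients in its last packet loses 1/3, 2/3 or 2/3 of a certain assignment relative to the one-third rate. The largest loss over six sites is 6 × 2/3 = 4, which leaves 22.7 of 80 (28.3%). For example, two left over at each site gives 12 patients in partial packets and 68 in 17 full ones, and 17 × 4/3 = 22.7.

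**Step 5: after the fix, with blocks of 4 and 6 equally likely.** For a block of 2m the certain share is 1/(m + 1), so a block of 6 has 1/4, or 1.5 assignments.

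- Size of each block known: (4/3 + 3/2)/10 = 28.3% certain.
- Sizes concealed (the coordinator knows at most that both sizes occur): about 5–6% certain, by simulation.
- Best guess: 41/60 = 68.3% for blocks of 6 alone. For the mix with sizes known it is (4 × 17/24 + 6 × 41/60)/10 = 69.3%. With sizes concealed it is about 68–69%, by simulation.

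**The case against.** The strongest reply is that the plan already separates knowledge from decision. The Investigator, who is blinded, decides entry; the coordinator may not share assignments and is given no decision on entry. The envelope is opened only after reconfirmation. A patient screened today will be randomised at least 28 days later, by which time others may have been randomised or dropped out, so at screening the coordinator cannot be sure of that patient's place in a packet. This stands. It confines usable foreknowledge mostly to the period around reconfirmation and the scheduling of first clinic visits, but it does not remove it.

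Picking at random from a shuffled packet also leaves the six orderings equally likely if it is done honestly. That is correct. The weakness is that nothing could show whether it was.

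Two stronger readings are tempting, and the documents do not support them:

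- *A third of assignments are predictable to the study team at large.* The certainty belongs only to someone who knows the earlier assignments in the packet. By protocol that is the coordinator. The Investigator lacks it unless assignments leak, and the documents give no evidence that they do.
- *The allocation leaves no record, so irregularities could not be found.* Designations are recorded, device files show what was delivered, and sites are audited. Each consecutive run of four can be checked for 2:2 balance. Only a pre-specified order within the packet is missing.

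A site manual might also hold numbering or a log. The protocol mentions neither, and opening at random does not fit with opening in numbered order.

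**Conclusion.** The point holds in limited form. In complete packets the coordinator knows one third of assignments before opening: about 27 of 80, and no fewer than about 23 if all six sites end on a partial packet. This assumes that the coordinator knows all earlier assignments at the site, and it counts the 80 planned completers, although more patients may be randomised. It measures opportunity and is not evidence that selection would occur.

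An audit could confirm balance and the device delivered, but not whether envelopes were chosen selectively within a packet. Sample size and endpoints are unaffected. This is a cheap improvement that the sponsor should make, not a fatal flaw. It also has a limit: someone who sees past assignments can still guess the under-represented arm, so best-guess accuracy barely moves. The main gains are fewer certain assignments and an order that can be checked.

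**What to change.** - In section 3, replace the hand-shuffled packets with a computer-generated list for each site, prepared off-site, with randomly varying block sizes (for example 4 and 6). Withhold the sizes from all site staff, including the coordinator, and take them out of the protocol that sites hold.
- Use sequentially numbered, opaque, sealed envelopes, opened strictly in order after the Investigator's reconfirmation has been recorded.
- In section 4(ii), replace the words *at random* with *in numbered order*.

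**Cost.** A new list and relabelled envelopes; no extra patients. An unfinished block can leave a site imbalance of up to 3 instead of 2. The gain depends on keeping the sizes concealed: if the size of each block becomes known, 28.3% of assignments remain certain. The unblinded coordinator would still take part in screening, so the change reduces the exposure and does not end it.

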Days 1 & 2: Completion of a set training module. A single treatment administered by the Pivotal Study coordinator with the subject following the treatment procedure closely. Both before and after the treatment the Pivotal Study coordinator will describe and demonstrate to the patient how a treatment procedure is initiated and successfully completed. At the end of the session the Pivotal Study coordinator will ask the patient to proceed as if she or he were providing a treatment to herself or himself, and the Pivotal Study coordinator will observe, monitor and instruct as advisable. If the Study Coordinator believes that the patient does not need a second day of training, a phone call interview can be conducted instead (in that case, the usability questionnaire should be completed on Day 1). If a second treatment day is used, a single treatment at the clinic administered by the subject with the Pivotal Study coordinator overseeing the treatment procedure closely and assessing the competence of the patient to self-treat is recommended. If the Pivotal Study coordinator concludes that the subject is ready, the subject will then be allowed to continue twice-daily treatments at home until the end of the Treatment Period. The patient will be instructed that if she or he has any questions or encounters any issues at home, the patient should immediately call the Pivotal Study coordinator. If the Pivotal Study coordinator concludes that the patient is not ready for selftreating at home and that additional training is needed, the patient will be instructed to return to the clinic the next day to receive such additional training. A usability questionnaire will be completed.

- Day 3-4: repeat the schema specified for Day 2 only if the subject needs additional training time.

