- During each of the clinic visits, the relevant Pivotal Study coordinator will (v) interview the subject, collect treatment delivery data from the CVS-M Device according to the schedule above and complete assessment forms. Collectively, data from the Daily Headache Diary, Quality of Life and Cognition Assessment and Visit Assessments will ensure assessment of safety and also coverage of all six core areas of assessment highlighted by Turk et al.: (1) pain; (2) physical functioning; (3) emotional functioning; (4) global ratings of satisfaction; (5) any negative health states and/or adverse events; and (6) subject disposition. Additionally, Visit Assessments and usability questionnaire forms will provide information to SNS with respect to satisfaction with the comfort, fit, operation, etc. of the CVS-M Device. At all times throughout the Study Period all subjects will have access to an Investigator or her/his designated Study coordinator by telephone, email and/or visit.

5) Active Treatment Parameters; Placebo Treatments

The following parameters will be set for active treatments using the CVS-M Device:

- A standardized CVS time-varying waveform lasting approximately 19 minutes will be used for all active treatment patients at all Pivotal Study sites. Treatments will be administered twice daily. The two daily treatments will be separated by at least one hour.
- The waveform schedule for active treatment patients will consist of a warm sawtooth delivered to one ear and a cold sawtooth delivered to the other ear. The warm sawtooth will go from body temperature to 42 °C, and the cold sawtooth will go from body temperature to 17 °C. The two waveforms will be delivered simultaneously, but will have different oscillation frequencies. After each two-day period, the warm and cold waveforms will be switched so that the opposite ears will be treated with the different caloric stimulation. Thus every two days the ear receiving the cold stimulus will be switched to the warm stimulus and vice versa.

The following parameters will be set for the placebo treatments using the CVS-M Device:

- A standardized CVS time-varying waveform lasting approximately 4 minutes will be used for all placebo treatment patients at all Pivotal Study sites. Treatments will be administered twice daily. The two daily treatments will be separated by at least one hour.

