- The waveform schedule for placebo treatment patients will consist of turning on the cooling fans and leaving the earpieces unpowered for a ~4-minute period.
- The earpiece tips will be covered with EVA rubber to prevent cooling of the ear canal by the metallic earpieces.

The Placebo Device will look identical to the Treatment Device and *will* show, on its screen, a time-varying waveform similar to that for an active treatment. The y-axis of the plot will be labeled "stimulation intensity" and will not list temperature values (the same will be true for the Treatment Device). A patient receiving a placebo treatment will have the sensation of the earpieces creating some pressure in the ear canals and may feel the earpieces warm up to body temperature. Placebo patients will not undergo material caloric vestibular stimulation since no temperature gradient will be created across the horizontal semicircular canal. (The threshold for therapeutic benefit using CVS has not been established, but even small temperature changes can result in nystagmus (Sedjawidata et al. & Vesterhauge et al.).) The term "CVS" will not be used in describing the Device to any patient and no reference to caloric stimulation will be made. The Device will be referred to as a neuromodulation device and the specific mechanism of action will not be disclosed to patients.

All patients will be told that they may or may not benefit from the Device in terms of

pain reduction and that, further, the point in the 3-month treatment period at which a change may be noticed is unknown and may vary from patient-to-patient – i.e., the treatment duration necessary for a potential reduction in pain is unknown for any particular individual. Patients will be told that they may or may not sense slight pressure from the earpieces, a warming or cooling sensation, or slight nausea or dizziness, especially at the end of the treatment session. At the conclusion of the Treatment Period, patients will be asked to identify which arm they believe they entered (active treatment or placebo).

6) Safety; Vestibular System Examination and Monitoring

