- **Migraine Headache Day** shall mean any calendar day during which a patient had a Migraine Headache of at least 30-minutes in duration.
- Month or Monthly shall mean or refer to a period of twenty-eight days, usually consecutive in timing.
- **Neuropsychologist** will be [name]., Duke U. Medical Center, Depts. of Medical Psychology and Medicine-Neurology, Durham, NC.
- **Pain Score** shall mean a maximal pain rating made by a subject for an individual Headache or for a Headache-Free Day based on using the Headache Pain Scale (zero to ten).
- **Pivotal Study** shall mean this SNS-sponsored, multi-site, randomized, triple-blinded, placebo-controlled, episodic migraine clinical study.
- **Pivotal Study Period** shall mean, with respect to each Pivotal Study participant, a period of 112 days beginning with the first day of the subject's Pre-Treatment Baseline Period and ending when she/he completes making recordings in her/his Daily Headache Diary at the end of the Treatment Diary Period (excluding the Enrollment Re-Confirmation Period and any gaps due to clinic scheduling issues). In outline, the Study Period will chronologically consist of the following:
 - Days 1-28 Pre-Treatment Baseline Period.
 - Whatever few days are required for the Enrollment Re-Confirmation Period (it may be possible to complete this enrollment re-evaluation on the first day during the clinic

Version 072414 Schulman Version 4

treatment week). Any time gap here is ignored in terms of listing the timeframe for the Pivotal Study.

- One to four days during which the patient comes to the clinic for treatments.
- Days 29 through 112 Treatment Period (includes days of treatment in the clinic).
- **Pivotal Study Sites** will be the Duke University Medical Center, the Naval Medical Center at San Diego, East Kent University Hospital & University of Kent in England, Michigan Headache and Neurological Institute, Carolina Headache Institute, and Headache Wellness Center.
- **Placebo Device** shall mean the SNS CVS-M Device wherein the earpieces are maintained at body temperature, thus eliminating any therapeutically meaningful CVS effect from operation of the Device.
- **Pre-Treatment Baseline Period** shall mean, with respect to each Pivotal Study participant, the first month (i.e., twenty-eight days) of the Pivotal Study Period for such patient.

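### Placebo sessions run about 4 minutes and active sessions about 19, so a difference between arms could not be attributed to caloric stimulation alone

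*Combined protocol and SAP*

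**What the plan says.** Section 5 (Active Treatment Parameters; Placebo Treatments) sets the two session lengths. For the active arm: "A standardized CVS time-varying waveform lasting approximately 19 minutes will be used for all active treatment patients". For the placebo arm: "A standardized CVS time-varying waveform lasting approximately 4 minutes will be used for all placebo treatment patients". The schedule is the same in both arms: "Treatments will be administered twice daily", with at least an hour between sessions. Section 4 gives a Treatment Period of 84 days.

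Section 5 describes the placebo session as "turning on the cooling fans and leaving the earpieces unpowered for a ~4-minute period", with rubber-covered tips to keep the metal from cooling the ear canal. Several other features are matched. The placebo unit looks the same, shows a similar waveform on its screen and carries the same axis label without temperatures. The mechanism is withheld from patients, and all patients get the same account of what they may feel and when. At the end of treatment they are asked which arm they think they were in. Session length is not among the matched features, and no reason for the difference is given.

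The Definitions describe the Placebo Device differently, as one in which "the earpieces are maintained at body temperature, thus eliminating any therapeutically meaningful CVS effect from operation of the Device".

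Section 9 states the null hypotheses for Migraine Headache Days and for Total Monthly Headache Pain as comparisons between the Treatment Device and the Placebo Device.

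**The concern.** A sham control supports a claim about a mechanism to the extent that it differs from the active treatment only in that mechanism. Here the arms differ in two respects: whether caloric stimulation is delivered, and how long each session lasts. Every active patient has the long session and every placebo patient the short one. Duration and stimulation are therefore completely confounded, and neither covariate adjustment nor a subgroup analysis can separate them. No third arm does so either.

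The outcomes make this worth attention. The Definitions leave it to the patient to decide whether a headache was a migraine, and the patient also scores the pain. Outcomes of that kind can in principle respond to features of a treatment other than its intended mechanism. At stake is the interpretation of a positive result: whether it supports the claim that the stimulation works, or only that the complete active regimen did better than a much shorter sham.

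**Working it through.** **Inputs.** Active session about 19 min and placebo session about 4 min (section 5); 2 sessions a day in both arms (section 5); 84 treatment days (section 4); a Month of 28 days (Definitions), with the third Month as the efficacy window (section 4(iii) and Definitions, Treatment Period).

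**The plan's own figures.** The plan gives no cumulative device time, so there is no such figure to reproduce. The nearest stated numbers are the cohort sizes in section 9. Alpha is not stated there; I assume 0.05 two-sided. The pooled two-proportion formula for 45% versus 15% at 80% power gives, per arm,

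n = [1.96 x sqrt(2 x 0.30 x 0.70) + 0.84 x sqrt(0.45 x 0.55 + 0.15 x 0.85)]² / 0.30² = about 35.4, rounded up to 36, so 72 in total.

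This matches the plan, and the other five rows (54, 44, 50, 40, 32) reproduce in the same way. Session length does not enter the calculation, so this point does not change the sample size.

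**Device time at full adherence.**

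- Sessions: 2 x 84 = 168
- Active: 168 x 19 / 60 = 53.2 h
- Placebo: 168 x 4 / 60 = 11.2 h
- Difference: 168 x 15 / 60 = 42.0 h; ratio 19 / 4 = 4.75
- Per day: 2 x 19 = 38 min against 2 x 4 = 8 min
- Third Month only: 56 x 15 / 60 = 14.0 h

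**Sensitivity of the 42 hours.**

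- *Clinic days.* On a training day section 4 describes "A single treatment administered by the Pivotal Study coordinator with the subject following the treatment procedure closely". The Definitions allow one to four clinic days. With one session on each, the total is 167 down to 164 sessions, and the difference is 167 x 15 / 60 = 41.75 h down to 164 x 15 / 60 = 41.0 h.
- *Approximate lengths.* Reading the per-session difference as 14 to 16 min (an assumption) gives 168 x 14 / 60 = 39.2 h to 168 x 16 / 60 = 44.8 h.
- *Adherence.* The documents state no adherence rate. At an assumed 70% to 90% in both arms, the difference is 0.70 x 42 = 29.4 h to 0.90 x 42 = 37.8 h.

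The imbalance is large on every reading.

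**What the contrast estimates.** Write the section 9 between-arm difference as S + D, where S is the effect of caloric stimulation and D is the effect of about 15 further minutes of device use per session. Each arm has one session length, so the data identify only S + D. The documents contain nothing from which D could be estimated.

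**The two sham descriptions.** Section 5 leaves the earpieces unpowered and says the patient may feel them warming to body temperature. The Definitions have them held at body temperature during operation. Both conclude that there is no meaningful caloric effect, but they do not describe the same condition at the start of a session.

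**The case against.** The strongest reply is that nothing in the documents shows that 15 further minutes with an inactive device changes migraine frequency. The comparison of the 19-minute package with the sham remains randomised and can be estimated without bias as a comparison of packages. The Definitions require the sham to lack a therapeutically meaningful caloric effect; they do not promise that everything else is equal. The matched appearance and display, the withheld mechanism and the common patient wording all bear on expectation, and the arm guess at the end gives some check on blinding. All of this stands. It limits how strongly the point can be put, but it does not equalise session length: patients who are perfectly blinded would still differ in device time.

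A reader might go further and infer that active patients get several times more daily rest, that the bias favours the device, or that some fixed share of the planned 30-point responder difference (45% versus 15%) comes from session length. The documents support none of these. They prescribe sessions and verify compliance from device time records, but they do not say that patients must rest or stop other activity. The advice to check balance before standing suggests that patients are seated, and no more than that. No figure in the plan anchors a size for a duration effect, and any honest range includes zero. Whether patients were told how long a session should last cannot be judged, because the consent pages are not in the public text.

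A further fair objection concerns the remedy. Section 5 supports the absence of material stimulation for a sham of about 4 minutes. It also notes that even small temperature changes can produce nystagmus and that the threshold for benefit is not established. A longer fan run cannot simply be assumed to be inert.

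Finally, the difference between the two sham descriptions is minor and does not bear on duration. Earpieces that reach body temperature and stay there could loosely fit both.

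**Conclusion.** The point holds as a limit on attribution. Session length differs completely by arm, no reason is given, and the active arm has about 42 hours more device time per patient over 84 days at full adherence (about 41 to 42 hours allowing for single-treatment clinic days; 14 hours in the third Month). The section 9 contrasts therefore estimate the 19-minute package against a 4-minute sham, and a difference could not be credited to caloric stimulation alone.

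This does not show that the result would be biased. The effect of duration on migraine days is unknown in size and direction and may be zero. The device-time figures rest on the stated session lengths, two sessions a day and full adherence; lower adherence reduces them in proportion. The confounding itself depends on none of these assumptions. It is an avoidable weakness in the control condition that is cheap to remove before treatment starts and cannot be repaired by analysis afterwards.

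**What to change.** 1. Match the clock time of the placebo session to that of the active session. Leave the active waveform unchanged, and keep the placebo earpieces unpowered and covered as section 5 now has them, with the fans and the screen display running for the full session.
2. Before adopting this, do a bench check that the longer fan run creates no temperature gradient at the covered earpieces.
3. If matching is not feasible, state the reason in section 5 and limit the conclusion in section 9 to the 19-minute package against the short sham.
4. Reconcile section 5 with the Placebo Device entry in the Definitions, so that the sham delivered is the sham defined.

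The cost is longer sessions for placebo patients (the same time the active arm already gives), a small bench check, a change to the placebo device's run time, and wording in section 5 and the Definitions. The sample size does not change.
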